8.3.2. Serious and Unexpected Suspected Adverse Reaction (SUSAR)

A serious adverse event is considered to be a suspected adverse reaction if there is evidence to suggest a causal relationship to the study agent. This may include a single occurrence of an event strongly associated with drug exposure (e.g. Stevens Johnson Syndrome), one or more occurrence of an event otherwise uncommon in the study population, or an aggregate analysis of specific events occurring at greater frequency than expected from historical controls.

Unexpected events are those not listed at the observed specificity or severity in the protocol, consent, Investigator brochure, or FDA-approved package insert. This includes adverse events listed in the protocol or consent as occurring within the class of drugs or otherwise expected from the drug's pharmacological properties but which have not been previously observed with this agent.

The lead institution (University of Chicago) is responsible for notifying all participating investigators, when required, and in accordance with applicable laws and regulations of any Expedited Safety Reports that are determined by the Lead Principal Investigator to be Unexpected.

8.3.3. Serious Adverse Event Reporting and Documentation Requirements

8.3.3.1. Serious Adverse Event Reporting to the University of Chicago

Use the UC CCC protocol number and the protocol-specific subject ID assigned during trial registration on all reports.

All serious adverse events (as defined above) occurring on this study require expedited reporting to the University of Chicago Comprehensive Cancer Center (UC CCC).

SAEs occurring at the University of Chicago as well as other sites, will be reviewed by the Lead Principal Investigator, who will determine whether they are SUSARs. The Lead Principal Investigator or designee will report all SUSARs to the UC CRA and UC CCC, who will report simultaneously to the UC IRB and other US sites, according to regulations (see below).

The responsible Research Nurse or other designated individual at the treating site should report the SAE to the Study Lead Investigator, the University of Chicago CRA and the UC CCC CCTO by the end of the business day when s/he becomes aware of the event. Events occurring after business hours should be reported to the CCTO by 12pm (noon) the next business day. Reports should be made using the 'Serious Event Report' Form. Please scan and send via email (preferred) or fax to the following:

University of Chicago Phase II CRA General: [contact] [contact]

[contact]

UC CCC Cancer Clinical Trials Office Quality Assurance: [contact]

All unexpected adverse reactions must be reported to the IND holder so that the University of Chicago CCTO can inform the FDA. The responsible Research Nurse or other designated individual at the treating site should provide a complete written report using the FDA MedWatch 3500A form. The completed form should be sent to the CCTO at [contact] and to the Phase II CRA at [contact] within the specified timelines below regardless of whether all information regarding the event is available. If applicable, a follow-up report should be provided to the CCTO if additional information on the event becomes available.

Fatal or Life-threatening Events: within 4 calendar days from treating investigator knowledge of the event

All Other Reportable Events: within 10 calendar days of treating investigator knowledge of the event.

All serious adverse events should also be reported to the local IRB of record according to their policies and procedures.

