6.8. Study Termination

Any Grade 5 toxicity related to study treatment will prompt stopping of the trial until further review is completed. Additionally, development of Grade 4 of non-hematologic toxicities in 2 or more patients will prompt the DSMB to stop the study for review to determine whether the trial should be terminated due to excessive toxicity.

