6.10.3. Tumor Lysis Syndrome

TLS, which may be associated with multi-organ failure, has been observed in treatment Cycles 1 and 2 in some subjects with MM who have been treated with carfilzomib. All subjects should follow the hydration guidelines outlined in Section 6.3.2. If subjects are considered to be at risk for TLS, hydration should be continued into Cycle 2 if clinically indicated.

MM subjects with high tumor burden (e.g., Durie-Salmon or ISS Stage II/III), rapidly increasing M-protein or light chains, or compromised renal function (CrCl < 50 mL/min) should be considered to be at particularly high risk.

During Cycles 1 and 2, serum electrolytes and chemistries are closely monitored. Subjects with laboratory abnormalities consistent with lysis of tumor cells (e.g. serum creatinine $\geq 50\%$ increase, LDH \geq 2-fold increase, uric acid $\geq 50\%$ increase, phosphate $\geq 50\%$ increase, potassium $\geq 30\%$ increase, calcium $\geq 20\%$ decrease) prior to dosing should not receive the scheduled dose. Subjects with such abnormalities should be re-evaluated as clinically indicated. The Lead Principal Investigator should be consulted if there are further delays.

If TLS occurs, cardiac rhythm, fluid, and serial laboratory monitoring should be instituted. Correct electrolyte abnormalities, monitor renal function and fluid balance, and administer therapeutic and supportive care, including dialysis, as clinically indicated.

All cases of TLS must be reported to the Lead Principal Investigator (who will, in turn be responsible for distributing this information to all sites) and to Amgen as a Serious Adverse Event (SAE) through the normal process within 24 hours of the clinical site becoming aware of the event.

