8.3. Serious Adverse Events

All SAEs will be collected by the UC CRA and reviewed by the Lead Principal Investigator. Only those determined to be SUSARs by the Lead Principal Investigator will be distributed to all participating sites (using the completed MedWatch 3500 form). To ensure subject safety, each serious adverse event must be reported to the Lead Principal Investigator and the University of Chicago Comprehensive Cancer Center via paper submission via fax or email within 24 hours of learning of its occurrence. A paper SAE form is provided for this study and may be used and sent via fax or email.

The Lead Principal Investigator is responsible for notifying the investigators of any expedited, annual, or other periodic safety reports in accordance with applicable regulations.

The Site Investigator is also responsible for notifying the local IRB in accordance with local regulations. Additionally, the Lead Principal Investigator is responsible for reporting SAEs to BMS and Amgen as described in section 8.4.

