8.4. Expedited Reporting by the Lead Principal Investigator to BMS and Amgen

The University of Chicago CRA will inform BMS and Amgen in writing by email or facsimile of any SAE occurring to US subjects within 24 hours of being aware of the event using a completed MedWatch3500 Form.

The date of awareness should be noted on the report. The initial report must be as complete as possible, including details of the current illness and (serious) adverse event, and an assessment of the causal relationship between the event and the investigational product(s). A final report to document resolution of the SAE is required.

SAE Reporting to Bristol-Myers Squibb (BMS)

The Overall PI, as study sponsor, will be responsible for all communications with the BMS. With the exception of any serious adverse event that meets the FDA's criteria for expedited reporting following the reporting requirements and timelines set by the FDA. The written report must be completed and supplied to BMS by facsimile or e-mail within 24 hours of Lead Principal Investigator knowledge of the event

- The BMS SAE form should be used to report SAEs. If the BMS form cannot be used, another acceptable form (ie, CIOMS or Medwatch) must be reviewed and approved by BMS. The BMS protocol ID number must be included on whatever form is submitted by the Sponsor/Investigator.
- Following the subject's written consent to participate in the study, all SAEs, whether related or not related to study drug, are collected, including those thought to be associated with protocol-specified procedures. The investigator should report any SAE occurring after these time periods that is believed to be related to study drug or protocol-specified procedure. For drugs with potential for delayed SAEs (eg, delayed excretion of the parent or active metabolites), a longer follow-up period may be warranted to allow collection of these SAEs, laboratory tests, and other assessments.

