11. DATA REPORTING

Data reporting will be performed utilizing the eVelos electronic data capture system for all subjects. The University of Chicago CRA will provide the applicable user registration information for all sub-sites.

All required data must be recorded in the eVelos database within two weeks of the completion of each cycle. AEs and SAEs are to be entered in eVelos in real time. SAEs are also to be recorded on the paper Serious Adverse Event Form within 24 hours of the site's knowledge of the event and sent via email (preferred) or fax to the University of Chicago ([contact] or [contact]; [contact]).

All case report forms must be completed by designated study personnel. Each screened subject (signed informed consent) is to be entered into eVelos within 48 hours of subject registration. In addition to direct data entry, providing supporting documentation is required as per Subject Enrollment and Registration policies. Source records are original documents, data, and records (e.g., medical records, raw data collection forms, pharmacy dispensing records, recorded data from automated instruments, laboratory data) that are relevant to the clinical trial. Each site will prepare and maintain adequate and accurate source documents. These documents are designed to record all observations and other pertinent data for each subject enrolled in this clinical trial. Source records must be adequate to reconstruct all data transcribed onto the case report form.

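### Section 8.3.3.1 lets after-hours SAEs wait until noon of the next business day, which over a weekend or holiday exceeds the 24-hour limit in 8.3, 11 and 13.5.3

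*Combined protocol and SAP*

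**What the plan says.** Three places set a 24-hour limit that runs from the site's knowledge.

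- Section 8.3 makes reporting of each SAE mandatory, with the lead investigator and the lead institution's cancer center as recipients. The route and deadline are: "via paper submission via fax or email within 24 hours of learning of its occurrence".
- Section 11 says "SAEs are also to be recorded on the paper Serious Adverse Event Form within 24 hours of the site's knowledge of the event", and that the form is then sent to the University of Chicago.
- Section 13.5.3 gives the same 24 hours for entering the SAE in the eCRF, in addition to the paper form.

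Section 8.3.1 then refers sites to 8.3.3 for reporting guidelines. There, 8.3.3.1 counts in business days. An SAE goes to the lead investigator, the CRA and the CCTO by the close of the business day on which the site becomes aware of it. For the rest of the week: "Events occurring after business hours should be reported to the CCTO by 12pm (noon) the next business day".

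Two other provisions bear on the timing. Section 6.10.3 requires every case of tumor lysis syndrome (TLS) to be reported to the Lead Principal Investigator and to Amgen "within 24 hours of the clinical site becoming aware of the event". Section 6.8 says "Any Grade 5 toxicity related to study treatment will prompt stopping of the trial until further review is completed". It also has the DSMB stop the study for review once Grade 4 non-hematologic toxicity has occurred in 2 or more patients.

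**The concern.** The section that sites are told to use for SAE reporting contains a deadline that can be longer than the one in 8.3, and the protocol does not rank them. A research nurse who opens 8.3.3.1 on a Friday evening finds permission to report at noon on Monday, even for a death.

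The two rules also differ in ways that make them hard to apply together. The noon sentence is keyed to when the event occurs, whereas 8.3 and 11 are keyed to when the site knows. It names only the CCTO, whereas 8.3 names the Lead Principal Investigator and the cancer center. The preceding sentence, which does name the lead investigator and the CRA, does not say what applies when awareness falls on a non-business day.

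What is at stake is the lead site's knowledge of serious events at 5 centers. A related death pauses the trial under 6.8, and the Grade 4 criterion is a count across sites. Neither can be acted on centrally before the report arrives. The scheduled safety teleconference in 13.7 is bi-weekly, so it does not replace prompt individual reports.

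**Working it through.** No sample size, error rate or event count enters this point. The check is elapsed time from the event to the deadline in 8.3.3.1, set against 24 hours.

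**Inputs from the protocol**

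- Limit in 8.3, 11 and 13.5.3: 24 h from site knowledge.
- After-hours limit in 8.3.3.1: 12:00 on the next business day.
- Business-hours limit in 8.3.3.1: close of the same business day.

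**Assumptions, since the protocol does not define business hours**

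- Close of business is 17:00, with a range of 16:00 to 18:00.
- The site becomes aware when the event occurs.
- For an event in the small hours of a weekday, the next business day is the one about to begin.

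**Longest allowance over an ordinary weekend**

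Friday 17:00 to Monday 12:00 = 7 + 24 + 24 + 12 = 67 h, which is 67 − 24 = 43 h beyond the limit. A 16:00 close gives 68 h and an 18:00 close gives 66 h.

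**With a Monday holiday**

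67 + 24 = 91 h (90 to 92 h over the same range of closing times).

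**Monday to Thursday evenings**

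17:00 to 12:00 the next day = 7 + 12 = 19 h (18 to 20 h). This is within 24 h.

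**Business-hours awareness**

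The report is due by close of the same day. With awareness at 09:00 and a 17:00 close that is 8 h, stricter than 24 h.

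**How much of an ordinary week is affected**

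The noon rule exceeds 24 h for events from Friday 17:00 until Sunday 12:00, because Sunday 12:00 to Monday 12:00 is exactly 24 h. That window is 7 + 24 + 12 = 43 h, and 43/168 = 25.6% of clock hours (42 to 44 h, or 25.0% to 26.2%). In the other 168 − 43 = 125 h (74.4%), 8.3.3.1 is at or below 24 h. These are shares of clock time, not of SAEs.

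**TLS**

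The clock in 6.10.3 starts at site awareness and runs 24 h. A report first made at 67 h is therefore 43 h late, and the lead site could not have forwarded it to Amgen in time.

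**The case against.** The best defense is that the rules can be obeyed together. Section 8.3 is worded as an obligation and 8.3.3.1 as an expectation, so a site that meets the earlier deadline satisfies both. The noon sentence extends the time only for the CCTO and does not release the site from telling the Lead Principal Investigator within 24 hours. Section 6.10.3 is a specific obligation of its own, which a general sentence elsewhere does not cancel. Section 11 also asks for SAEs to be entered in eVelos in real time, and 5.3.1 identifies eVelos as the University of Chicago database, so a second route exists.

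This limits the finding but does not remove it. The 67 hours arises only when 8.3.3.1 is followed alone, yet that is the section to which sites are referred, and no rule of precedence is given. Nothing says that an eVelos entry alerts the Lead Principal Investigator.

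A reader might infer more than the documents support:

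- **That the clocks for reporting to BMS and Amgen fail.** Section 8.4 has the University of Chicago CRA inform the companies "within 24 hours of being aware of the event using a completed MedWatch3500 Form", and its other company deadlines are tied to the Lead Principal Investigator's knowledge. A late site report delays the start of these clocks; it does not breach them. Only the TLS clock starts at the site.
- **That the 4- and 10-calendar-day MedWatch limits in 8.3.3.1 contradict 8.4.** Those limits are for unexpected reactions, sent by the site on Form 3500A so that the CCTO can inform the FDA. Sender, recipient, scope and form all differ from the step in 8.4.
- **That the 6.8 rule is disabled.** Section 6.8 states no time limit, so its reliance on prompt site reports is an inference, though a reasonable one for a count across centers.

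**Conclusion.** The inconsistency is real, stands in the current text and is not resolved elsewhere. Section 8.3.3.1 alone allows up to about 67 hours (66 to 68) over an ordinary weekend and 91 hours with a Monday holiday, against a stated limit of 24. This rests on an assumed close near 17:00, on occurrence and awareness coinciding, and on a site waiting until the last permitted moment.

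It would be wrong to conclude that 8.3.3.1 is generally the looser rule, or that any site following it is in breach. For business-hours awareness and for Monday to Thursday evenings it is as strict as 24 hours or stricter. The defect is limited to weekends and holidays.

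Within that window there are two consequences. The TLS deadline in 6.10.3 is missed outright, and the lead site's knowledge for the 6.8 review is delayed. The first follows from the text; the second is inferred. The point should be corrected, but it is a wording conflict in safety reporting and has no bearing on the efficacy analysis.

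**What to change.** In 8.3.3.1, keep the end-of-business-day sentence. Replacing it with a flat 24 hours would loosen reporting for most of the working week.

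Reconcile the noon sentence with 8.3 by adding a cap: and in any case within 24 hours of the site becoming aware, weekends and holidays included. Key that sentence to awareness instead of occurrence, and address it to the Lead Principal Investigator, the CRA and the CCTO, so that all SAE provisions share one clock start and one recipient list.

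State also that TLS reports under 6.10.3 follow the same site-awareness clock. The MedWatch 3500A limits and the company clocks in 8.4 need no change on this account.

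The cost is an amendment of a few sentences. Sites would sometimes have to send a form by email or fax at a weekend, which 8.3 already requires of them.

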8.3.3.2. Serious and Unexpected Adverse Event reporting by the University of Chicago

The designated UC CCC Regulatory Manager will notify all participating sites of all SUSARs that occur on this clinical trial and which are reported to the UC Institutional Review Board (IRB). A copy of the completed Form 3500 (MedWatch) will be distributed to all participating sites.

8.4. Expedited Reporting by the Lead Principal Investigator to BMS and Amgen

The University of Chicago CRA will inform BMS and Amgen in writing by email or facsimile of any SAE occurring to US subjects within 24 hours of being aware of the event using a completed MedWatch3500 Form.

The date of awareness should be noted on the report. The initial report must be as complete as possible, including details of the current illness and (serious) adverse event, and an assessment of the causal relationship between the event and the investigational product(s). A final report to document resolution of the SAE is required.

SAE Reporting to Bristol-Myers Squibb (BMS)

The Overall PI, as study sponsor, will be responsible for all communications with the BMS. With the exception of any serious adverse event that meets the FDA's criteria for expedited reporting following the reporting requirements and timelines set by the FDA. The written report must be completed and supplied to BMS by facsimile or e-mail within 24 hours of Lead Principal Investigator knowledge of the event

- The BMS SAE form should be used to report SAEs. If the BMS form cannot be used, another acceptable form (ie, CIOMS or Medwatch) must be reviewed and approved by BMS. The BMS protocol ID number must be included on whatever form is submitted by the Sponsor/Investigator.
- Following the subject's written consent to participate in the study, all SAEs, whether related or not related to study drug, are collected, including those thought to be associated with protocol-specified procedures. The investigator should report any SAE occurring after these time periods that is believed to be related to study drug or protocol-specified procedure. For drugs with potential for delayed SAEs (eg, delayed excretion of the parent or active metabolites), a longer follow-up period may be warranted to allow collection of these SAEs, laboratory tests, and other assessments.
- The Investigator will reconcile the clinical database SAE cases transmitted to BMS Global Pharmacovigilance ([name]). Frequency of reconcilliation should be on a quarterly basis and prior to the database lock or final data summary. BMS GPV&E will email upon request from the Investigator, the GPV&E reconcilliation report. Requests for reconcilliation should be sent to [contact]. The data elements listed on the GPV&E reconcilliation report will be used for case identification purposes. If the Investigator determines a case was not transmitted to BMS GPV&E, the case should be sent immediately to BMS.
- In accordance with local regulations, BMS will notify investigators of all reported SAEs that are suspected (related to the investigational product) and unexpected (ie, not previously described in the IB). In the European Union (EU), an event meeting these criteria is termed a Suspected, Unexpected Serious Adverse Reaction (SUSAR). Investigator notification of these events will be in the form of an expedited safety report (ESR).

- Other important findings which may be reported by the as an ESR include: increased frequency of a clinically significant expected SAE, an SAE considered associated with study procedures that could modify the conduct of the study, lack of efficacy that poses significant hazard to study subjects, clinically significant safety finding from a nonclinical (eg, animal) study, important safety recommendations from a study data monitoring committee, or sponsor decision to end or temporarily halt a clinical study for safety reasons.
- O Upon receiving an ESR from BMS, the investigator must review and retain the ESR with the IB. Where required by local regulations or when there is a central IRB/IEC for the study, the sponsor will submit the ESR to the appropriate IRB/IEC. The investigator and IRB/IEC will determine if the informed consent requires revision. The investigator should also comply with the IRB/IEC procedures for reporting any other safety information.
- In addition, suspected serious adverse reactions (whether expected or unexpected) shall be reported by BMS to the relevant competent health authorities in all concerned countries according to local regulations (either as expedited and/or in aggregate reports).
- An SAE report should be completed for any event where doubt exists regarding its seriousness.
- For studies with long-term follow-up periods in which safety data are being reported, include the timing of SAE collection in the protocol.
- If the investigator believes that an SAE is not related to study drug, but is potentially related to the conditions of the study (such as withdrawal of previous therapy or a complication of a study procedure), the relationship should be specified in the narrative section of the SAE Report Form.
- If only limited information is initially available, follow-up reports are required. (Note: Follow-up SAE reports should include the same investigator term(s) initially reported.)
- If an ongoing SAE changes in its intensity or relationship to study drug or if new information becomes available, a follow-up SAE report should be sent within 24 hours to BMS using the same procedure used for transmitting the initial SAE report. All SAEs should be followed to resolution or stabilization. All SAEs should be followed to resolution or stabilization.

All Serious Adverse Events (SAEs) that occur following the subject's written consent to participate in the study through 60 days of discontinuation of dosing must be reported to BMS Worldwide Safety. SAEs, whether related or not related to study drug, and pregnancies must be reported to BMS within 24 hours. SAEs must be recorded on BMS or an approved form; pregnancies must be reported on a Pregnancy Surveillance Form.

If only limited information is initially available, follow-up reports are required. (Note: Follow-up SAE reports should include the same investigator term(s) initially reported.)

If an ongoing SAE changes in its intensity or relationship to study drug or if new information becomes available, a follow-up SAE report should be sent within 24 hours to the BMS (or designee) using the same procedure used for transmitting the initial SAE report.

All SAEs should be followed to resolution or stabilization.

SAE Reporting to Amgen

The Lead Principal Investigator must inform Amgen in writing by e-mail or fax at the contact information listed below for all SUSARs that are judged as reasonably related to the Amgen study drug. Site will transmit the final MedWatch form of that event to Amgen within twenty-four (24) hours of Lead Principal Investigator knowledge of the event.

For regulatory reporting purposes, an event of "Death, Cause Unknown" from the study shall be processed as a SUSAR. All forms must be completed and provided to Amgen in English.

The Individual Case Safety Report (ICSR) may be referred to as an individual safety report or SAE Report, including Pregnancy Exposure Reports and Follow up Reports. The ICSR must be as complete as possible, at a minimum including event reference number, protocol name and number, investigator contact information, specific subject identifiers (e.g., initials, subject number, date of birth or age, or gender), the name of the suspect Study Drug, the date and dosage(s) of exposure, event, the date(s) of event, country of event, "Serious" Criteria, Relationship/causality of Study Drug, Hospitalization history for the event, Event status/outcome, Relevant history (including diagnostics, laboratory values, radiographs, concomitant medications, and event treatment, and narrative summary.

The Lead Principal Investigator shall be responsible for collecting all SAEs and Pregnancy and Lactation Exposure Reports and will exercise commercially reasonable due diligence to obtain follow-up information on incomplete SAE or Pregnancy and Lactation Exposure Reports. In the event that the Company requires clarification or further information on individual SAE or Pregnancy and Lactation Exposure Reports, Amgen will not contact non-party investigators directly, but will route all such inquiries through the Lead Principal Investigator for forwarding to such investigator(s). The Lead Principal Investigator will be responsible to ensure such inquiries are completed and timely provided to Amgen.

Information not available at the time of the initial report (e.g., an end date for the SAE, discharge summaries, lot numbers, relevant laboratory values, scan data and autopsy reports) which are received after the initial report must be documented on a follow-up form, and submitted to Amgen in the same timelines as outlined above. The Lead Principal Investigator shall be responsible for obtaining follow-up information for the SAEs and demonstrate diligence in attempting to obtain such information by, among other things, maintaining written records of such attempts.

Other aggregate analysis including reports containing safety data generated during the course of the study is to be submitted to Amgen at the time the Lead Principal Investigator submits to anybody governing research conduct i.e. IRB etc. Final study report and reports of unauthorized use of a marketed product to be submitted to Amgen at the time the Lead Principal Investigator ISS submits to anybody governing research conduct i.e. IRB etc. but not later than one calendar year of study completion.

Reports containing safety data generated during the course of the study is to be submitted to Amgen at the time the Lead Principal Investigator submits to anybody governing research conduct, i.e. IRBs. The Lead Principal Investigator will support reconciliation of all ICSRs at the end of the study at a minimum.

The Amgen protocol number (ISS # 20167383) and the institutional protocol number should be included on SAE reports to Amgen.

Amgen Safety Contact Information:

Fax: Toll-free US [contact]

[contact] (toll, global)

Drug Safety Reporting by secure e-mail can be established upon request.

